10.52 Death

Note: A death on study requires both routine and expedited reporting regardless of causality, unless as noted below. Attribution to treatment or other cause must be provided.

Any death occurring within 30 days of the last dose, regardless of attribution to an agent/intervention under an IND/IDE requires expedited reporting within 24-hours.

Any death occurring greater than 30 days with an attribution of possible, probable, or definite to an agent/intervention under an IND/IDE requires expedited reporting within 24-hours.

Reportable categories of Death

- Death attributable to a CTCAE term.
- Death Neonatal: A disorder characterized by cessation of life during the first 28 days of life.
- Death NOS: A cessation of life that cannot be attributed to a CTCAE term associated with Grade 5.
- Sudden death NOS: A sudden (defined as instant or within one hour of the onset of symptoms) or an unobserved cessation of life that cannot be attributed to a CTCAE term associated with Grade 5.
- Death due to progressive disease should be reported as **Grade 5** **"Neoplasms benign, malignant and unspecified (including cysts and**

polyps) – Other (Progressive Disease)" under the system organ class (SOC) of the same name. Evidence that the death was a manifestation of underlying disease (e.g., radiological changes suggesting tumor growth or progression: clinical deterioration associated with a disease process) should be submitted.

10.53 Secondary Malignancy

- A **secondary malignancy** is a cancer caused by treatment for a previous malignancy (e.g., treatment with investigational agent/intervention, radiation or chemotherapy). A secondary malignancy is not considered a metastasis of the initial neoplasm.
- All secondary malignancies that occur following treatment with an agent under an IND/IDE will be reported. Three options are available to describe the event:
 - Leukemia secondary to oncology chemotherapy (e.g., Acute Myelocytic Leukemia [AML])
 - Myelodysplastic syndrome (MDS)
 - Treatment-related secondary malignancy
- Any malignancy possibly related to cancer treatment (including AML/MDS) should also be reported via the routine reporting mechanisms outlined in each protocol.

10.54 Second Malignancy

A second malignancy is one unrelated to the treatment of a prior malignancy (and is NOT a metastasis from the initial malignancy). Second malignancies require ONLY routine reporting unless otherwise specified.

10.55 Pregnancy

Before study enrollment, subjects must agree to take appropriate measures to avoid pregnancy. However, should a pregnancy occur in a female study subject, consent to provide follow-up information regarding the outcome of the pregnancy and the health of the infant until 30 days old will be requested.

A female subject must immediately inform the Investigator if she becomes pregnant from the time of consent to 30 days after the last dose of study drug. A male subject must immediately inform the Investigator if his partner becomes pregnant from the time of consent to 3 months after the last dose of study drug. Any female subjects receiving study drug(s) who become pregnant must immediately discontinue study drug. The Investigator should counsel the subject, discussing any risks of continuing the pregnancy and any possible effects on the fetus.

Although pregnancy itself is not regarded as an adverse event, the outcome will need to be documented. Any pregnancy occurring in a subject or subject's partner from the time of consent to 30 days after the last dose of study drug must be reported. Any occurrence of pregnancy must be reported to Pharmacyclics

Drug Safety, or designee, per SAE reporting timelines. All pregnancies will be followed for outcome, which is defined as elective termination of the pregnancy, miscarriage, or delivery of the fetus. Pregnancies with an outcome of live birth, the newborn infant will be followed until 30 days old and this must be reported to Pharmacyclics Drug Safety, or designee, per SAE reporting timelines. Any congenital anomaly/birth defect noted in the infant must be reported as a serious adverse event.

10.6 Required Routine Reporting

10.61 Baseline and Adverse Events Evaluations

Pretreatment symptoms/conditions to be graded at baseline and adverse events to be graded at each evaluation per CTCAE v4.0 grading **unless** otherwise stated in the table below:

| System Organ Class (SOC) | Adverse event/Symptoms | Baseline | Each evaluation |
|--------------------------------------|---------------------------|----------|-----------------|
| Investigations | Platelet count decreased* | X | X |
| Blood and lymphatic system disorders | Anemia* | X | X |

*** Grading will be performed by the study statisticians at the time of analysis based on the CLL toxicity grading scale for blood counts in Appendix V. Anemia grade per CTCAE will also be recorded for reporting purposes.**

10.62 Submit via appropriate MCCC Case Report Forms (i.e., paper or electronic, as applicable) the following AEs experienced by a patient and not specified in Section 10.6:

10.621 Grade 2 AEs deemed *possibly, probably, or definitely* related to the study treatment or procedure.

10.622 Grade 3 and 4 AEs regardless of attribution to the study treatment or procedure.

10.623 Grade 5 AEs (Deaths)

10.6231 Any death within 30 days of the patient's last study treatment or procedure regardless of attribution to the study treatment or procedure.

10.6232 Any death more than 30 days after the patient's last study treatment or procedure that is felt to be at least possibly treatment related must also be submitted as a Grade 5 AE, with a CTCAE type and attribution assigned.

10.7 Late Occurring Adverse Events

Refer to the instructions in the Forms Packet (or electronic data entry screens, as applicable) regarding the submission of late occurring AEs following completion of the Active Monitoring Phase (i.e., compliance with Test Schedule in Section 4.0).

11.0 Treatment Evaluation

NOTE: Information from CT scans is not considered in the standard classification of response.

Note: Treatment-related lymphocytosis is a known phenomenon with ibrutinib and is not representative of PD. As noted in the Leukemia Research Foundation Workshop report⁵²: "Patients with lymphocytosis and no other evidence of PD should continue therapy until they develop other definitive signs of PD (i.e., at least one feature suggesting worsening of the CLL other than lymphocytosis (e.g., anemia, thrombocytopenia, lymphadenopathy, or hepatosplenomegaly) or the occurrence of another reason to discontinue therapy."

PD: "If PD is suspected, clinical examination, computed tomography, and peripheral blood counts should be obtained, and a bone marrow biopsy considered, to provide objective assessment of CLL status. Note: Recommended to be confirmed on two independent occasions at least 2 weeks apart and consistent with the IWCLL guidelines."

Note: Since this is a maintenance trial in which patients will be enrolled after having a clinical response from induction therapy, a further decrease in disease burden as noted by decrease in lymph node size or hepatosplenomegaly may not be observed. Thus, patients will be recorded with an objective status of "Not PD" as long as they do not demonstrate disease progression (or PD, defined below in section 11.2).

11.1 Overall Schedule of evaluations

(a) **Clinical Response:** Will be evaluated and documented at baseline (this is defined as the response to the induction therapy). Thereafter clinical response will be evaluated for progression of disease only every 3 cycles of study treatment (for 36 cycles) and every cycle (every 3 months) during follow-up period of without therapy for 2 years.

(b) **MRD status:** To be assessed at baseline (document positivity in blood or bone marrow) and then every 3 cycles of treatment (for 36 cycles) and thereafter every 3 months (for MRD-) and every 6 months (for MRD+) during follow-up without therapy for 2 years.

Note: Bone marrow aspirate done solely for MRD will be considered research. As outlined by the IWCLL guidelines a bone marrow biopsy / aspirate is required to document complete remission. Thus, a bone marrow biopsy / aspirate that is done as part of the clinical response to therapy (such as to document complete remission as part of clinical care as required by the IWCLL guidelines) will be considered standard of care. Additionally, if the bone marrow biopsy or aspirate is done as part of the clinical care of the patient (as determined by the treating physician) that procedure will be considered standard of care.

11.2 Evaluation for Progression of Disease

11.21 **PROGRESSION (PD):** Patients will continue to receive protocol therapy unless they have evidence of disease progression according to the IWCLL criteria⁶ as evidenced by:

11.211 $\geq 50\%$ increase in the sum of the products of at least 2 lymph nodes on 2 consecutive determinations 2 weeks apart (at least one node must be ≥ 2

cm) that persist for > 3 months or the appearance of new palpable lymph nodes >1.5 cm not due to a tumor flare. Enlargements or the appearance of new nodes due to a tumor flare do NOT qualify as progression.

- 11.212 $\geq 50\%$ increase in the size of the liver and/or spleen as determined by measurement below the respective costal margin on 2 consecutive determinations 2 weeks apart and with a minimum of a ≥ 2 cm increase in size from baseline; or appearance of hepatomegaly or splenomegaly which was not previously present at baseline and not due to a tumor flare.
- 11.213 Transformation to a more aggressive histology (e.g. Richter's transformation).

Note: If a patient develops DLBCL at any time, it will be considered disease progression. If the patient develops any other hematologic malignancy while on study, it will not be considered progressive disease.

- 11.214 $\geq 50\%$ increase in the absolute number of circulating lymphocytes NOT due to infection, tumor flare or drug-associated lymphocytosis (taking as reference for progressive disease the smallest absolute lymphocyte count recorded since the treatment started). The absolute lymphocyte count must be at least $5000/\text{mm}^3$ to qualify as disease progression.
- 11.215 In the absence of progression as defined by 1, 2, 3, or 4 above, the presence of a ≥ 2 g/dl decrease in HGB, or $\geq 50\%$ decrease in platelet count or absolute neutrophil count will NOT exclude a patient from continuing the study. Work-up of such decreases to exclude auto-immune hemolytic anemia, pure red cell aplasia, or idiopathic thrombocytopenic purpura (ITP) should be considered.
- 11.216 For patients who achieve a CR or nodular PR, progression will be defined as recurrence of circulating leukemia cell clone and an ALC >5000 or recurrence of adenopathy >1.5 cm not due to a tumor flare.

11.22 **Not PD:** The patient was evaluated for progression only in this cycle and a formal response evaluation did not occur. The patient did not meet the criteria for progression per section 11.21.

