Treatment related Lymphocytosis:

Similar to other agents targeting B-cell receptor signaling, transient lymphocytosis is a pharmacodynamic effect of ibrutinib, in which the inhibition of BTK-mediated cellular homing and adhesion results in a mobilization of tumor cells to the peripheral blood (Stevenson 2011).

A reversible increase in lymphocyte counts (ie, $\geq 50\%$ increase from baseline and above absolute count 5000/mcL), often associated with reduction of lymphadenopathy, has been observed in most subjects (approximately 69% to 75%) with CLL/SLL treated with single agent ibrutinib. This effect has also been observed in some subjects (33%) with

MCL treated with single agent ibrutinib. This observed lymphocytosis is a pharmacodynamic effect and should not be considered progressive disease in the absence of other clinical findings. In both disease types, lymphocytosis typically occurs during the first few weeks of ibrutinib therapy (median time 1.1 weeks) and typically resolves within a median of 8.0 weeks in subjects with MCL and 18.7 weeks in subjects with CLL/SLL.

Lymphocytosis appeared to occur in lower incidence and at lesser magnitude in subjects with CLL/SLL receiving ibrutinib in combination with chemoimmunotherapy (ie, 27% of subjects receiving ibrutinib + BR in Study 1108) or immunotherapy (ie, 55% of subjects receiving ibrutinib + ofatumumab in Group 2 of Study 1109).

A substantial increase in the number of circulating lymphocytes (e.g., >400,000/ μ L) has been observed in a subset of subjects. There have been isolated cases of leukostasis reported in subjects treated with ibrutinib. Bleeding-related events: There have been reports of hemorrhagic events in subjects treated with ibrutinib both with and without thrombocytopenia. These include primarily minor hemorrhagic events such as contusion, epistaxis, and petechiae; and some major hemorrhagic events including gastrointestinal bleeding, intracranial hemorrhage and hematuria.

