9.4 Treatment related lymphocytosis

Lymphocytosis has been reported with ibrutinib, however since this is a patient population who are already expected to be in remission post induction therapy it is not known if this lymphocytosis will still happen upon treatment with ibrutinib. Patients who develop this reaction will be monitored as per standard clinical protocol without specific intervention unless other specific symptoms / signs of disease progression is noted (such as increase in lymph node size that is progressive and persist beyond 3 months of

maintenance therapy, worsening of cytopenia from the time of initiation of maintenance therapy that is consistent with the IWCLL guidelines requiring therapeutic intervention, development of B symptoms persisting for more than 2 months while on therapy or other factors such as organomegaly demonstrating disease progression).

9.5

Medications to be used with caution

CYP3A-Inhibitors/Inducers: Ibrutinib is metabolized primarily by CYP3A. Avoid co-administration with strong CYP3A4 or moderate CYP3A inhibitors and consider alternative agents with less CYP3A inhibition.

If a strong CYP3A inhibitor (eg, ketoconazole, indinavir, nelfinavir, ritonavir, saquinavir, clarithromycin, telithromycin, itraconazole, nefazadone, or cobicistat) must be used, reduce ibrutinib dose to 140 mg or withhold treatment for the duration of inhibitor use. Subjects should be monitored for signs of ibrutinib toxicity.

If a moderate CYP3A inhibitor (eg, voriconazole, erythromycin, amprenavir, aprepitant, atazanavir, ciprofloxacin, crizotinib, darunavir/ritonavir, diltiazem, fluconazole, fosamprenavir, imatinib, verapamil, amiodarone, or dronedarone) must be used, reduce ibrutinib to 140 mg (for 840 mg/day dose, reduce to 280 mg) for the duration of the inhibitor use. Avoid grapefruit and Seville oranges during ibrutinib/placebo treatment, as these contain moderate inhibitors of CYP3A (see Section 5.3.1.2).

No dose adjustment is required in combination with mild inhibitors.

Avoid concomitant use of strong CYP3A inducers (eg, carbamazepine, rifampin, phenytoin, and St. John's Wort). Consider alternative agents with less CYP3A induction.

A comprehensive list of inhibitors, inducers, and substrates may be found at <http://medicine.iupui.edu/clinpharm/ddis/main-table/>. This website is continually revised and should be checked frequently for updates.

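### The progression rule for patients in CR or nodular PR lacks the drug-lymphocytosis exclusion given in 11.0 and 11.214, so one patient can be scored both PD and Not PD

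*Combined protocol and SAP*

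**What the plan says.** Section 11.216, for patients who reach CR or nodular PR: "progression will be defined as recurrence of circulating leukemia cell clone and an ALC >5000 or recurrence of adenopathy" larger than 1.5 cm, with tumor flare excluded for the nodes. Appendix XII C.6 repeats it.

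Section 11.214, the general lymphocyte criterion, counts a rise of at least 50% to at least 5000/mm³ only when it is "NOT due to infection, tumor flare or drug-associated lymphocytosis".

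The note at the head of Section 11.0 states: "Treatment-related lymphocytosis is a known phenomenon with ibrutinib and is not representative of PD". It is not limited by response category. The background (Section 1.2, treatment-related lymphocytosis) agrees: "This observed lymphocytosis is a pharmacodynamic effect and should not be considered progressive disease in the absence of other clinical findings". So does Section 9.4: "Patients who develop this reaction will be monitored as per standard clinical protocol without specific intervention unless other specific symptoms" or signs of progression appear.

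On how often this may happen, the background says the effect "has been observed in most subjects (approximately 69% to 75%) with CLL/SLL treated with single agent ibrutinib". For the trial's own population, already in remission, Section 9.4 says "it is not known if this lymphocytosis will still happen upon treatment with ibrutinib".

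**The concern.** Two provisions of the same section give different answers for a CR or nodular-PR patient whose lymphocyte count rises on ibrutinib without other signs of worsening. The PD call matters. Under 13.1 it moves the patient to event monitoring, where Section 18.1 lists only the event-monitoring form, so scheduled MRD testing stops. It also decides who enters the 48-week landmark analyses (16.323, 16.324) and, after the landmark, who has a PFS event.

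**Working it through.** **Provisions side by side**

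| Provision | Applies to | Lymphocyte condition | Drug lymphocytosis excluded? |
|---|---|---|---|
| 11.0 note | all patients | – | yes |
| 11.214, Appendix XII C.4 | all patients | rise of at least 50%, to at least 5000 | yes |
| 11.216, Appendix XII C.6 | CR, nodular PR | recurrent circulating clone and ALC >5000 | not stated |
| Appendix XII table, PD column | all patients | rise of at least 50%, to at least 5,000 | not stated |

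Footnote 6 of the Appendix XII table points to Section 11.23, which the current Section 11.2 does not contain, so the table does not bring the exclusion in by reference. The appendix does refer to 11.0 on lymphocytosis, but under the PR criterion (B.1).

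**How Not PD is decided.** Section 11.0 refers to 11.2 for the definition of PD, and 11.22 makes Not PD depend on no 11.21 criterion being met. Section 11.216 is one of those criteria. Section 11.1(a) takes the baseline response from induction, so 11.216 plausibly applies from the start of maintenance to a patient enrolled in CR. The documents do not say so outright; I assume it.

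**One patient, two scores.** Take a patient in CR with MRD in the marrow only, which 3.17 permits. CR requires lymphocytes below 4000/µL (Appendix XII A.4); let the baseline and lowest on-treatment count be 3,900. The background attributes the drug effect to tumor cells moving into the blood. Let the count reach 1.5 × 3,900 = 5,850 with a clone now detectable, and nothing else changed.

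- Background definition (at least 50% above baseline and over 5000): met.
- 11.214: numeric condition met, excluded as drug-associated, so not PD.
- 11.216: clone present and ALC >5000, no exclusion, so PD.
- 11.0 note: not PD.

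**Timing.** The first scheduled progression check is after 3 × 28 = 84 days, or 12 weeks. The background gives a median onset of 1.1 weeks and a median resolution of 18.7 weeks in CLL/SLL. Even counted from onset, 1.1 + 18.7 = 19.8 weeks. So the 12-week check falls before median resolution, and median resolution falls well before the 48-week landmark. A typical false call would come before the landmark. Confirmation two weeks apart is only recommended, and two weeks is short against 18.7.

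**Design figures.** With 32 evaluable patients and success at 4 or more, P(X ≥ 4 | 32, p) is 0.0738, 0.3997, 0.7279 and 0.9069 at p = 0.05, 0.10, 0.15 and 0.20. These reproduce the 0.07, 0.40, 0.73 and 0.91 in 16.24, and a wording change alters none of them.

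As illustration only, suppose a fraction f of would-be successes were removed before confirmation, so that p = 0.20 × (1 − f). The documents give no value for f; it is my assumption.

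| f | p | P(X ≥ 4) |
|---|---|---|
| 0 | 0.20 | 0.91 |
| 5% | 0.19 | 0.88 |
| 10% | 0.18 | 0.85 |
| 20% | 0.16 | 0.78 |
| 30% | 0.14 | 0.67 |

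**The case against.** The strongest reply is that the 11.0 note precedes all the PD criteria, is not limited by response category, and agrees with the background and 9.4. Only 11.216 read alone makes isolated drug lymphocytosis PD. As to intent, that stands: an investigator reading the whole protocol would probably follow 11.0. It does not remove the conflict. Section 11.216 is the more specific rule, 11.22 makes it binding, and because 11.214 restates the exclusion, its absence from 11.216 can be read as deliberate.

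A second reply is that 11.216 needs recurrence of a circulating clone, whereas a clone that never left the blood has persisted. That is fair for patients with blood MRD at entry, for whom the term is undefined. It does not help where the blood was negative and the marrow positive.

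Several stronger inferences are not supported:

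- A reader might take the effect as expected here, or apply 69% to 75% to this trial. That range is from single-agent ibrutinib in CLL/SLL generally, and 9.4 calls occurrence in this population unknown.
- A reader might infer that each false PD adds a PFS event. Under 16.324, patients who discontinue before 48 weeks are excluded, so an early call removes the patient instead.
- A reader might infer that the primary endpoint is lost. It is MRD-based, does not use the PD definition, and a response already confirmed still counts.
- A reader might call the rule stricter for deep responders. It drops the 50% rise: 3,900 to 5,001 is 1,101/3,900 = 28% and meets its count condition. But it adds a clone condition that 11.214 lacks.

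**Conclusion.** The inconsistency is real and should be reconciled. As written, 11.216 and Appendix XII C.6 can classify as PD a patient whom 11.0 classifies as not PD. The likely intent is visible elsewhere in the protocol, so this is not evidence that the plan means to count the drug effect as progression.

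The consequences are conditional on lymphocytosis occurring in a CR or nodular-PR patient and on 11.216 being applied literally. The patient would then go to event monitoring and could lose the chance of an MRD-negative response not yet confirmed. Before 48 weeks the patient would leave both landmark analyses; after the landmark, a false PFS event could be counted.

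No expected number of affected patients can be derived, because the documents give neither the rate in remission nor the share of patients in CR or nodular PR. The fall in power from 0.91 to between 0.88 and 0.67 shows sensitivity over an assumed 5% to 30% loss of successes; it is not an estimate. The fixed threshold of 4 in 32 leaves little room for avoidable losses.

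**What to change.** Reconcile 11.216, Appendix XII C.6 and the PD column of the Appendix XII table with 11.0 and 11.214, so that one stated treatment of drug-associated lymphocytosis governs every PD call and every PFS event. Which clinical rule that should be is for the study team.

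In the analysis, list any CR or nodular-PR patient called PD on lymphocyte count alone, with the date relative to week 48 and MRD status at the time. Add a PFS sensitivity analysis only for such calls after the landmark, scoring the call as an event and then as no event. For earlier calls it would change little, because a patient already off treatment stays outside the landmark set under either reading; listing them is enough.

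The cost is about one sentence in each of two places and a note to the table. Sample size, decision rule and data collection are unchanged.
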